Patients will be asked to arrive at the study site approximately 2 hours prior to dosing on Day 1. Patients in Cohort 1 will be randomized in a 2:1 ratio to receive the starting dose of 0.03 mg LJN452 or placebo. Safety assessments will be performed for 4 hours post dose and pharmacokinetic [REDACTED] assessments will be performed for up to 8 hours post first dose (see [Assessment schedule](#) for details). Prior to discharge, the patients will be given a supply of LJN452 or placebo and instructed to take first thing in the morning with water, prior to eating every day.

Patients will then return on Days 7, 14 and 21 for safety, pharmacokinetic [REDACTED] assessments and dosing. Patients will be asked to return to the study site on Day 28, for the final dosing visit, when safety, pharmacokinetic [REDACTED] assessments will be performed. Patients will be asked to return to the study site for an optional ambulatory visit on Day 29, where 24 hour post dose pharmacokinetic [REDACTED] assessments will be performed.

Patients are asked to return to the study site on approximately Day 56 for follow up assessments. An end of study visit will take place at approximately Day 84.

A dose escalation review and an interim analysis are planned when at least 12 patients have completed dosing and Day 28 assessments in Cohort 1. The main purpose of the interim analysis will be to evaluate the observed variability in GGT levels and, if needed, consider a sample size re-estimation.

The Lead PI from each active country and Investigators with patients recruited into the cohort will be invited to be involved in the review of blinded data from that cohort and the decision on the dose for the next cohort of subjects (if applicable). Full details of the process are outlined in the Dose Escalation Charter and the SOM.

Additional cohorts will follow the same schedule as Cohort 1. Further cohorts may be added depending on emerging safety and PK/PD data. Additional interim analyses may be performed after a minimum of 12 patients in each cohort finish dosing and Day 28 assessment. The sponsor will be unblinded and the Clinical Trial Team may be unblinded when all subjects in a cohort have completed 28 day of study hence at the time of the planned IAs.

Part 2

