Approximately 88 patients with PBC, with an incomplete biochemical response to, but still taking, UDCA or those not currently taking UDCA are planned to be recruited into Part 2, with the aim that 80 will complete the study. Patients who participated in Part 1 may be recruited to Part 2, provided they meet all required eligibility criteria and have not received study medication within 3 months of Randomization, (or longer if required by local regulations) – see exclusion criteria.

Figure 3-3 Study design Part 2

Week	-12 to -2	1	2	3	5	9	13	17
Study visit	↑	↑	TC	↑	↑	↑	↑	↑
Screening		←	-----	12 week treatment period	-----→		Follow up	EOS

BL = Baseline assessments (performed pre-dose Day 1)

↑ = Study visit

TC = Telephone Contact

EOS = End of Study visit

A screening visit will take place, where patient's eligibility to enter the study will be assessed.

Eligible patients will be asked to arrive at the study site approximately 2 hours prior to dosing on Day 1 to perform Baseline assessments.

Patients will be randomized in a 3:3:2 ratio to receive either LJN452 Dose level 1, LJN452 Dose level 2 or placebo. Following drug administration, safety, pharmacokinetic [REDACTED] assessments will be performed at two hours post dose.

Prior to discharge, the patients will be given a supply of LJN452 or placebo and instructed to take their dose first thing in the morning with water, prior to eating every day. New supplies will be dispensed on a monthly basis during regular study visits.

Patients will then return at weeks 3, 5, 9 and 13 for safety, tolerability, pharmacokinetic [REDACTED]. A telephone contact will be made one week after start of dosing to check their progress and check they have no questions.

Patients will be asked to return to the study site in week 17 for follow up assessments and to complete their end of study assessments.

If a patient has a medically important AE that is considered related to study drug and which has not resolved or stabilized at their scheduled end of study visit (week 17), they will be followed, until resolution or stabilization of the AE.

The following will be considered as medically important:

- i) An AE with CTCAE Grade ≥ 3
- ii) SAE
- iii) hepatic and renal events should be followed up per the guidance in [Table 15-1](#) and [Table 16-1](#)

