- Positive antimitochondrial antibodies (AMA) titer or if AMA negative or in low titer (<1:80) PBC specific antibodies (anti-GP210 and/or anti-SP100 and/or antibodies against the major M2 components (PDC-E2, 2-oxo-glutaric acid dehydrogenase complex))
- Previous liver biopsy findings consistent with PBC

4. At least 1 of the following markers of disease severity:

- ALP $\geq 1.67 \times$ upper limit of normal (ULN)
- Total bilirubin $>$ ULN but $< 1.5 \times$ ULN

In addition, patients must meet the following biochemical criteria at enrollment

- ALT or AST $\leq 5 \times$ ULN
- Total bilirubin $\leq 1.5 \times$ ULN
- INR \leq ULN

5. Subjects must weigh at least 40 kg to participate in the study, and must have a body mass index (BMI) within the range of 18 - 40 kg/m². BMI = Body weight (kg) / [Height(m)]².

6. Able to communicate well with the investigator, to understand and comply with the requirements of the study.

4.1.1 Additional Inclusion Criteria for Part 1

All patients enrolled in Part 1 must meet the following criteria:

1. Taking UDCA for at least 12 months, or for at least 6 months and has reached maximal response to UDCA with a plateau in alkaline phosphatase, (with no changes in dose for ≥ 3 months) prior to Day 1.

4.1.2 Additional Inclusion Criteria for Part 2

All patients enrolled in Part 2 must meet the following criteria:

1. Patients not currently taking UDCA and who have not taken UDCA for ≥ 3 months prior to Day 1 (for example UDCA naïve patients, patients who were unable to tolerate UDCA or had stopped taking due to lack of efficacy) OR Patients taking UDCA for at least 12 months, or for at least 6 months and has reached maximal response to UDCA with a plateau in alkaline phosphatase, (with no changes in dose for ≥ 3 months) prior to Day 1

4.2 Exclusion criteria for Parts 1 and 2

Patients fulfilling any of the following criteria are not eligible for inclusion in this study. No additional exclusions may be applied by the investigator, in order to ensure that the study population will be representative of all eligible patients.

1. Presence of other concomitant liver diseases including:
 - Active Hepatitis B or C virus (HCV, HBV) infection
 - Primary sclerosing cholangitis (PSC)
 - Alcoholic liver disease
 - Definite autoimmune hepatitis
 - Nonalcoholic steatohepatitis (NASH)

- Gilbert's Syndrome

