> 2 × ULN if normal baseline or >2 x baseline if elevated before drug exposure (in the absence of known Gilbert syndrome)	
 • Repeat tests^a within 48 hours of notification of result • Test for hemolysis (e.g., reticulocytes, haptoglobin, unconjugated [indirect] bilirubin) 	↑	Both Parts 
 • Discontinue study drug • Initiate close monitoring (evaluate 2-3 times a week with repeat tests^a) • Hospitalize if clinically appropriate • Establish causality and complete liver event checklist (in SOM) 		Both Parts 
 • Continue monitoring with Repeat tests^a until resolution^c
> 1.5 to ≤ 2 × ULN (patient is asymptomatic)	
 • Repeat tests^a within a week of notification of result 	↑	Both Parts If elevation from baseline is confirmed, initiate close observation of the patient i.e. evaluate 2-3 times a week with repeat tests ^a		Both Parts 
 • Repeat tests^a within 1 to 4 weeks or at next visit

Criteria	First Action	Result	Second Action	Result	Third Action
Jaundice	
 • Discontinue study drug • Initiate close monitoring (evaluate 2-3 times a week with repeat tests^a) • Hospitalize if clinically appropriate • Establish causality and complete liver event checklist (in SOM) 		Both Parts 
 • Continue monitoring with Repeat tests^a until resolution^c 		
Any AE potentially indicative of a liver toxicity*	
 • Consider study drug interruption or discontinuation • Hospitalization if clinically appropriate • Establish causality and complete liver event checklist (in SOM) 		Both Parts Investigator discretion		

*These events cover the following: hepatic failure, fibrosis and cirrhosis, and other liver damage-related conditions; the non-infectious hepatitis; the benign, malignant and unspecified liver neoplasms

^a Repeat tests: Physical examination and PT/INR and LFT: Liver function test: ALT, AST, GGT, alkaline phosphatase, total bilirubin, and albumin (see [Section 6.2.1](#));

^b(General) malaise, fatigue, abdominal pain, nausea, or vomiting, or rash with eosinophilia

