^cResolution is defined as an outcome of one of the following: (1) return to baseline values, (2) stable values at three subsequent monitoring visits at least 2 weeks apart, (3) remain at elevated level after a maximum of 6 months, (4) liver transplantation, and (5) death.

Elevation confirmed or persisting, i.e. remain > 90% of the original elevated level

Decreasing elevation, i.e. decrease to ≤ 90 % of the original elevated level.

Table 15-2 Renal events: definition and follow up requirements

Renal Event	Actions
Serum creatinine $\geq 2 \times$ BL or ≥ 1.5 mg/dL	
1. Hold study medication
 
2. Confirm increase after 24-48h of notification of the value
 
3. If confirmed, permanently discontinue study medication
 
4. Follow up until resolution or stabilization of laboratory abnormality(ies)

Serum creatinine increase 25 – 49% compared to baseline during normal hydration status	
Confirm 25% increase after 24-48h of notification of the value
 
Follow up within 2-5 days

Serum creatinine increase $\geq 50\%$ compared to baseline	
Confirm $\geq 50\%$ within 24-48 hours after receipt of the abnormal value
 
If confirmation of abnormal value is not possible in this timeframe study drug must be withheld until further evaluation is possible
 
Consider drug interruption
 
Consider patient hospitalization / specialized treatment

Albumin- or Protein-creatinine ratio increase ≥ 2 -fold compared to baseline	Confirm value after 24-48h of notification of the value
Albumin-creatinine ratio (ACR) ≥ 30 mg/g or ≥ 3 mg/mmol;	Perform urine microscopy
New dipstick proteinuria $\geq 1+$	Consider drug interruption / discontinuation
Protein-creatinine ratio (PCR) $>$ ULN	
New dipstick glucosuria $\geq 1+$ not due to diabetes	
Blood glucose (fasting)
 
Perform serum creatinine, ACR

New dipstick hematuria not due to trauma	
Urine sediment microscopy
 
Perform serum creatinine, ACR

Document contributing factors: co-medication, other co-morbid conditions, and additional diagnostic procedures performed in the CRF	
Monitor patient regularly (frequency at investigator's discretion) until one of the following: Event resolution: (sCr within 10% of baseline or protein-creatinine ratio within 50% of baseline) Event stabilization: sCr level with $\pm 10\%$ variability over last 6 months or protein-creatinine ratio stabilization at a new level with $\pm 50\%$ variability over last 6 months.	

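### Table 15-1's two bilirubin rows do not meet when baseline bilirubin is raised: an isolated value above 2 × ULN and up to 2 × baseline falls in neither row, although a lower value requires a repeat within a week

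*Protocol*

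**What the plan says.** Table 15-1 in Appendix 1 of the protocol has two rows for total bilirubin.

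- **Upper row:** "> 2 × ULN if normal baseline or >2 x baseline if elevated before drug exposure (in the absence of known Gilbert syndrome"). It requires a repeat within 48 hours and a hemolysis test. If the elevation is confirmed, study drug is discontinued and the patient is evaluated 2-3 times a week.
- **Lower row:** "> 1.5 to ≤ 2 × ULN (patient is asymptomatic"). It requires a repeat within a week of notification. If the rise from baseline is confirmed, the patient is evaluated 2-3 times a week, and the third action is a repeat "within 1 to 4 weeks or at next visit".

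A table footnote defines confirmation: "Elevation confirmed or persisting, i.e. remain > 90% of the original elevated level".

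Section 4.1 admits patients with raised bilirubin by design. One of the two markers of disease severity is "Total bilirubin $>$ ULN but $< 1.5 \times$ ULN", and the enrollment limit is "Total bilirubin $\leq 1.5 \times$ ULN". Section 4.2, exclusion 15, removes those whose bilirubin is above ULN with albumin outside the normal range. Gilbert's syndrome is excluded in Section 4.2, so that qualifier in the upper row has little effect.

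On visits, Section 3.1 says for Part 1 "Patients will then return on Days 7, 14 and 21 for safety, pharmacokinetic" and other assessments, with the final dosing visit on Day 28. For Part 2 it says "Patients will then return at weeks 3, 5, 9 and 13 for safety, tolerability, pharmacokinetic" and other assessments. Table 8-2 places the Part 2 visits on Days 15, 29, 57 and 85, each with liver function tests.

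**The concern.** The upper row depends on the patient's baseline; the upper limit of the lower row does not. When baseline is normal the two rows share a boundary at 2 × ULN. When baseline is raised, the upper row's threshold moves up to 2 × baseline while the lower row still ends at 2 × ULN, and a band opens between them.

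Read literally, the table then asks for less at a higher bilirubin than at a lower one. The documents give no reason for that ordering. Section 9.3 calls for a standard process in which liver laboratory triggers lead to repeat tests, and a value in the band has no bilirubin trigger. At stake is a possible delay in repeating an isolated bilirubin rise in a patient who is still taking the drug.

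**Working it through.** The documents give no figure to reproduce here; the check is whether the two rows cover every value. Let b be baseline bilirubin and v the on-treatment value, both in multiples of ULN, with baseline taken as elevated when b > 1.

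**Conditions (Table 15-1)**
- Upper row: v > 2 if b ≤ 1; v > 2b if b > 1.
- Lower row, asymptomatic: 1.5 < v ≤ 2 at every b.
- Matching neither, among asymptomatic values above 1.5: none if b ≤ 1; 2 < v ≤ 2b if b > 1.

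**Size of the band**
- Width = 2b − 2.
- Rise from baseline needed to enter it = 2/b − 1. The band ends at a 100% rise.

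| Baseline (× ULN) | Uncovered band (× ULN) | Width | Rise that lands in it |
|---|---|---|---|
| ≤ 1.0 | none | 0 | none |
| 1.1 | >2.0 to 2.2 | 0.2 | >82% to 100% |
| 1.3 | >2.0 to 2.6 | 0.6 | >54% to 100% |
| 1.5 | >2.0 to 3.0 | 1.0 | >33% to 100% |

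**One patient, baseline 1.3 × ULN, asymptomatic**
- v = 1.8 (1.8/1.3 = 1.38, a 38% rise): lower row, repeat within a week.
- v = 2.4 (2.4/1.3 = 1.85, an 85% rise): neither row.
- v = 2.7 (2.7/1.3 = 2.08, a 108% rise): upper row, repeat within 48 hours and discontinuation if confirmed.

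**Order of values.** If the same patient is first seen at 1.8 and the repeat is 2.4, then 2.4/1.8 = 133%. That is above 90% of the original value, so the elevation is confirmed and close observation begins. The gap therefore needs the first value above 1.5 × ULN to fall directly in the band.

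**Wait for the next scheduled test**
- Part 1, Days 1, 7, 14, 21, 28: intervals of 6, 7, 7 and 7 days. During dosing the schedule itself gives a repeat in about a week.
- Part 2, Days 1, 15, 29, 57, 85: intervals of 14, 14, 28 and 28 days. A first band value on Day 15 waits 14 days. On Day 29 or Day 57 it waits 28 days on drug. The Day 85 test is about 24 hours after the Day 84 dose (Table 8-2, note 5), so dosing is over.

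The assured difference in Part 2 is thus a repeat within 7 days of notification against a next scheduled test up to 28 days after the sample. The 2-3 tests a week under the lower row have no stated duration, so they are not counted.

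**The case against.** The strongest reply is that a patient in the band is not left unwatched.

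- **Other Table 15-1 rows.** The rows for ALT or AST above 2 × baseline and for ALP call for repeat tests or stronger action. Where they require a repeat it is due within 48 hours, and those tests include total bilirubin. The Hy's law row also applies at bilirubin above 2 × ULN, but only with ALT or AST above 3 × ULN and no ALP increase to above 2 × ULN. The jaundice and liver-AE rows need a clinical finding or an event.
- **Section 8.4.4.** Above 1.5 × ULN, direct and indirect bilirubin should be differentiated. Clinically relevant deviations must be discussed with the sponsor and repeated.
- **Oversight.** Section 7.1 lets the investigator stop treatment, Table 8-2 provides unscheduled visits, and Section 10.3 provides medical monitor and DMC review of laboratory data.

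This stands as a limit on scope: the point concerns an essentially isolated bilirubin rise, and many investigators would repeat the test anyway. It does not close the gap. Section 8.4.4 gives no interval, and no other provision sets a timed repeat for an isolated value in the band.

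A reader might infer that the lower row's restriction to asymptomatic patients is a second error and should be deleted. The documents do not settle that. In the ALT/AST rows symptoms lead to a stronger action, so the restriction may be meant to keep symptomatic patients out of the mildest tier, with the liver-AE row and Section 7.1 available for them. Deleting it would place them in that tier.

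**Conclusion.** The gap is real and follows from the current table text. For a baseline b above 1 × ULN, an isolated value above 2 × ULN and up to 2b × ULN matches neither bilirubin row, and the resulting order of actions is inverted. The band is at most 1.0 × ULN wide at the enrollment limit of 1.5 × ULN. In Part 2, eligibility is confirmed at screening (Section 6.1.1), so a Day 1 baseline that has risen since then would widen it.

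The practical effect is modest. It requires a raised baseline with normal albumin at screening, a first value above 1.5 × ULN that lands in the band, and no other liver row triggered. It is then felt mainly on Days 29 and 57 of Part 2. The number of such patients is unknown, because the documents give no bilirubin distribution; given these conditions it is probably small. The waits assume visits on their nominal days.

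Two stronger readings should be avoided. One is that patients in the band go unmonitored, or that every Part 2 patient faces a 28-day wait; the provisions and visit dates above do not support either. The other is that the discontinuation threshold for raised baselines is itself a mistake. Section 7.4 uses the same baseline-relative bilirubin threshold in the Part 1 cohort stopping rules, so it looks deliberate.

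**What to change.** In Table 15-1, change the upper limit of the lower bilirubin row to: *≤ 2 × ULN if normal baseline, or ≤ 2 × baseline if elevated before drug exposure*. Keep its first action as a repeat within a week at the latest; the sponsor may choose a shorter interval for values above 2 × ULN. Leave the discontinuation thresholds unchanged.

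Check: with T = 2 when b ≤ 1 and T = 2b when b > 1, the lower row becomes 1.5 < v ≤ T and the upper row remains v > T. The rows meet at T for every baseline, with no overlap. At baseline 1.3, a value of 2.4 would then require a repeat within a week.

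How to handle symptomatic patients above 1.5 × ULN is a separate choice for the sponsor and is not part of this change.

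Cost: one table edit by amendment, with the usual sponsor, ethics and, where required, health authority approvals (Section 13.1), and a few extra liver tests. No extra patients are needed and the analysis does not change.

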## 1 Introduction to RAP documentation

### 1.1 Scope

The RAP documents contain detailed information to aid the production of Statistics & Programming input into the Clinical Study Report (CSR) for trial “**CLJN452X2201**”.

**Module 3 (M3) provides the description of the statistical methodology** used to analyze the data, **TFL shells** details the presentation of the data, including shells of summary tables, figures and listings, and **Module 8 (M8)** contains programming specifications e.g. for derived variables and derived datasets, to support the creation of CSR outputs.

### 1.2 Changes to RAP documentation (M3)

Refer to corresponding guidances and NIBR RAP Addendum template for detailed information on the requirements of documenting changes to RAP documentation.

**For the statistical methodology (M3),** any major changes to the statistical methodology should be reflected in the RAP M3 documentation via version control (M3 amendment) (new document version to be approved by the trial team as the original module).

Such major changes could include (but are not limited to):

- change in statistical methodology
- substantial change in (derivation of) main endpoint
- substantial change in study design (e.g. protocol amendment introducing new multiple-dose cohorts in a so far single-dose trial)

Such changes may also require a protocol amendment to ensure consistency. In addition they need to be mentioned (high-level) in the CSR (section for changes to planned analysis).

Minor changes to the RAP M3 documentation can be captured e.g. by a study note to file / note in RAP Addendum or within the CSR itself.

Corrections of typographical errors or modification of spelling (from English to American, for example) do not need to be incorporated into the RAP M3 documentation.

This RAP M3 Amendment 1 is to reflect the following changes:

- The addition of a deviation code leading to exclusion from the PD analysis set in Table 5-1.
- The addition of the time by log-transformed baseline term in the repeated measures analysis model in Section 7.1.3.
- The changes to the study design in protocol amendment 5.

## **2 Study objectives and design**

[figure not shown]
### **2.1 Study objectives**

#### **2.1.1 Primary Objectives**

- To determine the effect of LJN452 on cholestatic markers (Liver function tests, specifically GGT) in patients with Primary Biliary Cholangitis (PBC). More specifically, in Part 2 to determine the dose-response relationship of LJN452 on GGT following 12 weeks of treatment
- To determine the safety and tolerability of daily dosing of LJN452 in patients with PBC

#### **2.1.2 Secondary Objectives**

- To evaluate the pharmacokinetics (PK) of LJN452 in patients with PBC
- To evaluate the change in overall disease specific quality of life from PBC40
- To determine the change in the itch domain of PBC40 questionnaire
- To evaluate the change in itch based on 100 mm visual analog score (VAS)
- Part 2: To determine the dose-response relationship of LJN452 on ALP in patients with PBC following 12 weeks of treatment

### **2.2 Study design and treatment**

[figure not shown]
This is a randomized, double-blind, placebo-controlled, multi-part study to assess safety, tolerability and efficacy of LJN452 in patients with Primary Biliary Cholangitis (PBC).

Part 1 uses an escalating multiple dose design in PBC patients with incomplete biochemical response to, but still taking, ursodeoxycholic acid (UDCA).

Part 2 is a parallel group, 12-week study to assess the safety, tolerability and efficacy of two doses of LJN452 compared to placebo in PBC patients with an incomplete biochemical response to, but still taking, UDCA or those not taking UDCA. The two LJN452 doses for Part 2 will be selected based on safety, tolerability and efficacy data from Part 1.

Once approximately 40 patients from Part 2 have completed 8 weeks of treatment, an interim analysis will be conducted to re-assess the sample size for Part 2. [Figure 2-1](#) shows how Parts 1 and 2 are connected.

**Figure 2-1** Study design

### Part 1

A minimum of 2 and maximum of 5 cohorts of approximately 15 patients with PBC with incomplete biochemical response, but still taking UDCA treatment will be enrolled into Part 1, with the aim of a minimum of 12 patients per cohort completing. Patients withdrawing for reasons other than AEs may be replaced throughout the study. Patients withdrawing from a cohort may not be enrolled in a subsequent cohort.

[Figure 2-2](#) shows the study design of Part 1. At the beginning of Part 1, a screening visit will take place, where a patient's eligibility to enter the study will be assessed. Eligible patients will be admitted to the study site and re-evaluated for inclusion / exclusion criteria during the baseline visit. All baseline safety evaluation results must be available and reviewed prior to first dosing.

